1. To gather additional safety and efficacy data and reaffirm that using the CVS device leads to a significant reduction in migraine headache days relative to a placebo.
2. To extend the treatment period from 3-months to 6-months, with all subjects (including placebo) receiving active treatment in the second 3-month period.
3. To test the efficacy of once-per-day active treatments versus twice-per-day active

treatments.

4. To evaluate the durability of gains realized after the end of the treatment period through an additional 3-month long headache diary period.

All participants will be subjects whose response to prior therapies has been partially successful, but limited. As defined in detail below, under International Headache Society (IHS) guidelines all of these subjects will be classified as “episodic” or acute. None will be classified as “chronic.” In assessing the effectiveness of the CVS device, the study will consider both (1) a subject’s number of headaches as well as (2) the severity of each and of all of those headaches. The primary endpoint is based on outcomes data collected during the treatment period vs. the pre-treatment baseline period, focusing on the comparative number of migraine headache days.

Description of the Treatment Paradigm and Study

1) Intended Use/Indication for Use

- **Intended Use:** The CVS device is intended to stimulate the vestibular system via external ear canals using controlled thermal waveforms.
- **Indication for Use:** The CVS device is indicated for use in the prevention of episodic migraine headache.

2) Subject Selection Criteria Pre-Treatment Data

In working with and through their respective designated assistant(s)/coordinator(s), the principal investigators will identify and screen potential participants, all of whom will have previously been diagnosed as episodic migraine headache subjects. The investigators will review the subjects' medical records to select those individuals who they identify as meeting the inclusion criteria for participating in the study.

- **Inclusion Criteria:** Each participant must have a pre-treatment history that, when initially screened by a principal investigator or designee, documents that she/he meets all elements of the following:

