 - The subject must have been diagnosed with episodic migraine headache at least six months prior to entering into the Study, consistent with the International Headache Classification of Headache Disorders (ICHD-II and ICHD-III beta) guidelines.
 - The subject must have a history of at least three consecutive months of stable migraine headaches prior to entering the study. The subjects will not have had changes in medication usage (prescription medications for migraine headache) for the three months leading up to the study, nor will they introduce new medications during the study period. (The primary focus is on prescription medications for migraine headache. However, medications that are prescribed for co-morbid conditions which also have

demonstrated efficacy for migraine prevention should not be altered in this time period.)

- Subjects will satisfy these criteria: On a monthly basis, at least four, and not more than a total of fourteen (4-14), headache days of which between four and fourteen (4-14) are migraine headache days, as judged by the subject.
- The subject must not have failed on more than two classes of properly administered prophylactic pharmaceutical therapies for migraine headache. The subject may be on a single migraine prophylactic drug as long as the dosage has not been altered within three months of starting the study and the dosage must not be altered for the duration of the study;
- The Investigator must have confidence in the subject's ability to reliably use the CVS device and promptly complete the electronic daily headache diary forms. The daily headache diary will be completed from the beginning of the pre-treatment baseline period through the end of the study. The diary is described more fully below and in the definitions section at the end of this document.

• **Exclusion Criteria:** Individuals who:

- have previously participated in a clinical trial using the CVS Device
- are pregnant
- using more than one concurrent prophylactic pharmaceutical therapy for migraine headache
- have a history of cardiovascular disease
- work night shifts
- have been diagnosed with vestibular migraine
- have menstrual migraine exclusively
- have been diagnosed with post-traumatic migraine
- have a history of unstable mood disorder or unstable anxiety disorder. Specifically, a BDI-II score of 20 or greater and/or a BAI score of 16 or greater will disqualify a patient from randomizing into the treatment portion of the study.
- use a hearing aid

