- have a cochlear implant
- have chronic tinnitus
- have temporomandibular joint disease
- have been diagnosed with traumatic brain injury
- have been diagnosed with neurological disease other than headaches

- have a diagnosed vestibular dysfunction and/or balance dysfunction
- have a history of abusing alcohol or other drugs
- are experiencing medication overuse headaches (individuals with respect to whom the principal investigator is concerned that analgesic abuse is involved based on the ICHD-II guidelines).
- are less than 18 years old or greater than 65 years old
- have had eye surgery within the previous three months or ear surgery within the previous six months
- have active ear infections or a perforated tympanic membrane
- have participated in another clinical trial within the last 30 days or are currently enrolled in another clinical trial
- are using Botulinum toxin-based treatments for migraines or for facial cosmetic reasons.
- are taking anti-emetics chronically (more than 2 times per week, consistently)
- Though not excluded, subjects taking anti-histamines will be encouraged not to take such medications within four hours prior to a CVS treatment. The investigator should review other medications taken by the subject with properties that mimic anti-nausea or anti-dizziness drugs as these may reduce responsiveness of the vestibular system to caloric stimulation. Such medications should also be avoided within four hours prior to a CVS treatment.

- **Withdrawal Criteria**

- Subjects must be withdrawn from the clinical trial if any of the following events occur:
 - Surgery during the study period.
 - A subject does not continue to meet inclusion/exclusion criteria.
 - A subject is significantly non-compliant with the requirements of the protocol (principal investigator & sponsor decision).
 - The subject does not complete at least 25 of 28 daily diary entries in her/his headache diary during the baseline period. (That is, the subject must be compliant with maintaining the headache diary.)
 - A subject becomes pregnant during the trial as evidenced by a positive pregnancy test.
 - The subject develops an illness (adverse event) that would interfere with his/her continued participation.
 - The subject withdraws his/her consent.
 - The principal investigator feels that it is the subject's best interest to be withdrawn.
 - Scion Neurostim discontinues the study or has achieved the targeted enrollment.

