If the subject is discontinued from the participation in the study for any reason, the principal investigator must make every effort to perform all evaluations for the final visit and document the reasons for discontinuation. If a subject withdraws due to an adverse event, the study coordinator will follow up with regular phone calls to document the resolution of the event.

Though a subject will not be withdrawn from the study if she/he exceeds 14 headache days in any of the treatment months, such subjects will be grouped separately during the final study analysis. The rationale for this grouping is that a large percentage of subjects in the first CVS migraine RCT were excluded from randomization because they exceeded 14 headache days, thus calling into question their stable episodic status. If a subject has a “good month” during baseline, but is potentially unstable, she/he might be recruited into the study in violation of the aim of enrolling stable EM subjects. No evidence that the CVS device increased headache burden was seen in the first RCT. However, we will continue to follow subjects who exceed 14 headache days in a month during the treatment period so as to gather more data on this sub-population.

- **Concomitant Medications**

- The use of acute abortive medications for the symptomatic treatment of migraine headache will be allowed during the clinical trial. Subjects may use their usual acute abortive medications, and medications should not be changed during the clinical trial. A treated migraine headache is one for which a subject has taken an acute abortive medication (prescription medication, not OTC).
- The subject may be on a single migraine prophylactic drug as long as the dosage has not been altered within three months of starting the study and the dosage must not be altered for the duration of the study. The subject must not have failed on more than two classes of properly administered prophylactic pharmaceutical therapies for migraine headache. Prophylactic medications used to treat other medical conditions may be used, at the principal investigator's discretion, if the subject is taking a stable dose for at least three months prior to screening and continues throughout the study.

3) Pivotal Study Size; Randomization

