The study period will last 280 days (plus additional visit window days, as needed), beginning with a pre-treatment baseline period of one month (28 days), at the end of which the principal investigator will reconfirm the appropriateness of the subject's participation in the study, followed by a first treatment period of three months (84 days), followed by a second treatment period of three months (84 days), followed by a post-treatment diary period of three months (84 days).

As noted, subjects will be advised that during the study period they may maintain patterns of usage of approved therapeutic medications that they normally use and that they should not initiate new medications, medicating patterns or other interventions. Accommodations for rescue medications will be made.

The study will be segmented with the following aims:

1. Baseline period and the first 3-month treatment period: **This portion of the study will be viewed as a complete RCT in-and-of itself and will be analyzed while the remainder of the study is still underway. The primary endpoint applies to this portion of the study.** Subjects will use an electronic data capture system that records headache pain level, duration and associated symptoms, acute medication use, and whether the headache was a migraine headache. Also, subjects will record any occurrence of an adverse event (AE).
2. Months 5-7 (from the start of the baseline period): All subjects will be assigned to the active device. Subjects will treat with the same frequency as they did in the first 3-month treatment period (e.g., BID in the first period means BID in the second period). Subjects will record the occurrence of a headache and whether

the headache was a migraine headache. Subjects will report any adverse events to the unblinded site coordinator.

3. Months 8-10 (from the start of the baseline period): Subjects will no longer be treating with the CVS device. Subjects will record the occurrence of a headache and whether the headache was a migraine headache. Subjects will report any adverse events to the unblinded site coordinator.

The phases and activities of the study are listed below:

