- To assess whether CVS therapy provides durable migraine prevention after therapy has ceased, the number of migraine days, the reduction in subject-perceived headache pain scores, the number of acute (prescribed) medication taken, during each month in the post-Tx observation period will be compared to both baseline and the final treatment month in all 3 treatment groups. The normalized percent-change in monthly headache days and the 50% responder rates (relative to baseline) will also be assessed. Additionally, the QOL measurements (HIT-6, BDI, BAI and Pittsburgh Sleep Quality Assessment scores) at the final visit will be compared to both the baseline and the 6 month scores.
- Measures of body mass index for each subject will be calculated at baseline, after three and six months of treatment and after the post-treatment observation period and compared across the three treatment

arms.

- Measures of depression (Beck Depression Inventory) and anxiety (Beck Anxiety Inventory) for each subject will be calculated at baseline, after three and six months of treatment and after the post-treatment observation period and compared across the three treatment arms.
- To assess whether the reduction in migraine days relates to the number of active CVS treatments performed, correlational analyses will be performed to assess whether the change in the total number of headache days during defined study periods (first treatment period, second treatment period and post-treatment observational period) is a function of the cumulative CVS treatments performed. Additionally, approaches such as the GLIMMIX procedure for generalized linear mixed models will also be performed to determine the probability of a headache on any given day is predicted by the cumulative number of active treatments performed.

As noted above, the baseline period and the first 3-month treatment period will constitute a complete RCT. Those data will be analyzed when the targeted number of subjects (120) complete the first treatment period. Subjects will continue on to the second 3-month treatment period without interruption, as they progress through the study period. For additional clarity, the stated primary endpoint will be evaluated for the baseline period + first 3-month treatment period.

[figure not shown]
8) Statistical Analysis and Study Size

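### Durability (months 8–10): the plan points to withdrawing a subject who starts a migraine preventive and has no rule if that subject is kept; either way lasting benefit can be overstated, probably modestly.

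*Combined protocol and SAP*

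**What the plan says.** Aim 4 (Background) is "To evaluate the durability of gains realized after the end of the treatment period through an additional 3-month long headache diary period". The durability endpoint in section 7 takes migraine days, pain scores and acute medication and says that these "during each month in the post-Tx observation period will be compared to both baseline and the final treatment month in all 3 treatment groups". It adds percent change, the 50% responder rate and the questionnaire scores.

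Four provisions bear on a preventive started after the device is returned:

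- Inclusion Criteria (section 2): prescription migraine medication must be stable before entry, "nor will they introduce new medications during the study period".
- Study Schedule (section 4): "The study period will last 280 days", and that total includes the 84-day post-treatment diary period.
- Withdrawal Criteria (section 2): "Subjects must be withdrawn from the clinical trial if any of the following events occur", and one listed event is "A subject does not continue to meet inclusion/exclusion criteria".
- After discontinuation for any reason, the investigator "must make every effort to perform all evaluations for the final visit". Continued diary entry is not asked for.

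The week 30–38 and Visit 6 forms say that preventives should not be changed. If one has been, the instruction is to add it to the concomitant medication form.

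Section 8 applies intent-to-treat to the primary aim, limits diary endpoints to subjects with at least 25 entries in the month, and gives no missing-data method. For months 5–7, section 4 states: "All subjects will be assigned to the active device".

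**The concern.** The durability question is how much of the gain is lost after stopping. Subjects whose migraine returns are the most informative about that, and they are also the likeliest to be offered a preventive. A rule that removes them, or one that keeps them without saying how on-drug months count, makes the reported loss too small and the responder rate too high.

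No concurrent comparison would show this. The comparisons are within group, and by month 8 the former placebo arm has also had three months of active treatment. Since the device is handed back at Visit 5, withdrawal in these months ends no device exposure. It only ends outcome collection.

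**Working it through.** **Timeline.** Week w covers study days 7(w−1)+1 to 7w.
- The observation period is weeks 29–40, days 197–280. Month 10 is weeks 37–40, days 253–280.
- The week-38 call falls on days 260–266. A subject withdrawn then has at most 266 − 253 + 1 = 14 month-10 entries, short of 25.
- A start on days 197 to 260–266 (64–70 of 84 days, 76–83%) can be reported by that call.
- Section 8 words the 25-entry rule for a treatment month, so its use in month 10 is itself a reading. If it does not apply, nothing says how a part-month counts.

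**The plan's own figure.** Section 8 gives a detectable difference of 2.13 days with 40 per arm, SD 3.36, 80% power and α = 0.05. A two-sided two-sample t calculation gives 2.131, so it reproduces. That figure concerns the month-3 contrast between arms. None is given for durability.

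**Numbers at month 10.** From 40 per arm, the expected loss of 5 per group per three months gives 35 at device return and 30 at month 10. The standard error of a group mean is 3.36/√30 = 0.61 days, assuming that the month-3 SD still applies.

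**If starters are withdrawn.** Let d of the five dropouts be subjects who relapsed and started a preventive. Assume those who stay hold the 3.6-day gain of the first trial, and that those withdrawn have lost D = 1.8 days (half) or 3.6 days (all). Overstatement of the mean = d/(30+d) × D. For responders, assume 15/30 = 50% is reported; counting the starters gives 15/(30+d).

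| d | Responder rate with starters counted | Points lower | Mean overstated (days) | In standard errors |
|---|---|---|---|---|
| 1 | 15/31 = 48.4% | 1.6 | 0.06–0.12 | 0.1–0.2 |
| 2 | 15/32 = 46.9% | 3.1 | 0.11–0.23 | 0.2–0.4 |
| 5 | 15/35 = 42.9% | 7.1 | 0.26–0.51 | 0.4–0.8 |

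Relative to 3.6 days this runs from 0.06/3.6 ≈ 2% to 0.51/3.6 ≈ 14%.

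**If starters are kept.** Assume a drug effect of e = 1–3 days per 28 days, a figure not in the documents. With the whole of month 10 on drug, the mean is raised by d × e/(30+d):
- one subject: 1/31 to 3/31 = 0.03–0.10 days;
- two subjects: 2/32 to 6/32 = 0.06–0.19 days.

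A start after the week-38 call covers only 14–20 of the 28 days. It adds (14/28 × 1)/30 = 0.02 to (20/28 × 3)/30 = 0.07 days per subject.

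**Effect on a within-group test.** A simulation assumed no true lasting gain, SD 3.36 and 35 per group, with withdrawal correlated with poor outcome. The chance of a falsely significant benefit, nominally 2.5%, was:
- 2 withdrawn: 4.0%, 5.4% and 7.3% at correlations 0.3, 0.5 and 0.7;
- 5 withdrawn: 6.4%, 11.2% and 18.6% at the same correlations.

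**The case against.** The strongest reply is that withdrawal is inferred. No sentence orders it for a preventive started in months 8–10. The generic trigger cannot be applied literally to every criterion: entry also requires at least four headache days a month, so a literal reading would expel good responders. Significant non-compliance is a separate trigger left to the investigator and sponsor, and a medication breach could go that way. The observation-period forms say only to record the drug, whereas the Visit 2 and Visit 4 forms spell out exit where exit is meant. All of this stands, so a reader should not infer that the plan expressly orders withdrawal.

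It does not close the gap. The medication clause looks forward, since it can only be broken after entry. The one written exemption, for exceeding 14 headache days, covers treatment months only. If sites keep such subjects, the bias comes through on-drug diaries instead, and sites may differ.

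Other parts of the reply also stand:
- Questionnaire scores are collected at early termination, and a late leaver still contributes earlier observation months. The loss is of diary data.
- The disposition form separates lack of efficacy from protocol violation, which helps in counting cases.
- Subjects on a stable preventive from before entry remain, so month 10 does not represent only people who need no drug.
- The table of the concomitant medication form is not visible in the supplied text, so it cannot be said that start dates go unrecorded.
- Barring new drugs off device has a sound purpose, which is to keep durability unconfounded.

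**Conclusion.** The point holds as a gap worth closing in a secondary aim. The linked clauses lead to withdrawal, the forms to retention, and section 8 handles neither; under both, durability can look better than it is. The direction rests on the assumption that preventives are started mainly because migraine has returned, and under retention also on the drug having some effect.

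The size is not fixed, because the documents give no rate of preventive starts. With 1–2 withdrawn starters per group it is about 0.06–0.23 days, under 0.4 standard errors. The upper figures, 0.51 days and 7.1 responder points, need all five expected dropouts to be starters who return fully to baseline. A reader might infer that the durability result would be largely an artefact. The documents do not support that: the simulated error rates assume no lasting effect at all, and the larger ones need five outcome-related withdrawals per group. Nor is the primary result in doubt, since month 3 precedes these events.

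**What to change.** 1. **Withdrawal Criteria:** state that after Visit 5 a new or changed migraine preventive is recorded but is not a reason for withdrawal, and that the diary continues to day 280.
2. **Section 8:** count such a subject as not a durable responder from the month the drug starts. Report mean migraine days as recorded, with a sensitivity analysis that uses the subject's baseline value for those months. Baseline substitution imposes full loss of benefit, so it should not be the main result.
3. **Reporting:** give the number of such subjects per arm. The rule needs the start date, so confirm that the medication form captures it.

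The cost is one sentence in the withdrawal criteria and a few in section 8. No subjects or visits are added, because the diary and two-weekly calls are already scheduled up to the week-40 visit. The change has to be in place before subjects reach the observation period, since diary days not collected cannot be recovered. The downside is that a preventive started for another condition would count as loss of durability in the responder analysis; the as-recorded means offset this.

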The design size contemplates enrolling up to one hundred and twenty (120) subjects who will successfully follow through to completion of their participation in at least the first treatment portion of the study (first 3-month treatment period). The subjects will be randomly assigned to: twice-per-day active, once-per-day active or twice-per-day placebo in a 1:1:1 ratio.

The results of the first migraine RCT did not show evidence of stratification based on gender or clinical site or baseline headache frequency. Envelopes containing

randomization assignments will be grouped in batches of six, each batch containing two of each of the three assignment arms. The batches of envelopes will be randomly shuffled by an agent not involved with the study. A given batch will be completed before the next batch is opened. This procedure results in 20 possible different arrangements, for six subjects, of the ordering of treatment and placebo assignments. The unblinded coordinator will record the subject's designation but will not share the assignment with the subject, principal investigator, or statistician. Each study site will be individually randomized (no central randomization).

The assessment of the primary endpoint will be completed by a blinded, central statistician. The subjects will be told, within the informed consent document, of the existence of a placebo arm. Subjects will be told that the device stimulates the brain stem. Subjects will be told that they will receive at least 3-months of active treatment during the 6-month treatment period. In fact, subjects in the placebo arm in the first 3-month period will be switched to active in the second 3-month period. Subjects will be asked to guess (and provide reasons) about their treatment assignment at the end of the first 3-month treatment period and at the end of the second 3-month treatment period. Subjects will also be asked, after their very first treatment in the clinic, a series of questions designed to assess the quality of blinding (to provide evidence that the placebo device is an effective sham).

4) Study Schedule; Subject Enrollment and Activities

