Note: The treatment delivery data (recorded on the SD cards) from the CVS device consists of temperature waveform files that contain actual measured temperature values that were delivered to the earpieces during treatments. This data is an independent record of the expected device performance and is used for confirmation purposes only. The SD card data files also record treatment times and subject compliance, which will be used to calculate the level of treatment compliance. Subjects will *not* be informed that the device monitors treatment compliance.

- **End of Second Treatment Period – Start of Observation Period:** At the end of the second treatment period, all subjects will return their devices to the clinics. The SD cards will be collected. Subjects will be asked to complete the QOL questionnaires again and will be asked to complete a final usability questionnaire.

Subjects will then be asked to continue to make recordings in their headache diaries for an additional 12 weeks.

- **End of Observation Period/End of Study:** Subjects will return to the clinics one final time. They will be asked to complete the QOL questionnaires.

5) Active Treatment Parameters; Placebo Treatments

The following parameters will be set for active treatments using the CVS device:

- A standardized CVS time-varying waveform lasting approximately 19 minutes will be used for all active treatment subjects at all study sites. Treatments will be administered once or twice daily, based upon a subject's randomization assignment. The two daily treatments should ideally be separated by at least one hour.
- The waveform schedule for active treatment subjects will consist of a warm sawtooth delivered to one ear and a cold sawtooth delivered to the other ear. The warm sawtooth will go from body temperature to 42 °C, and the cold sawtooth will go from body temperature to 17 °C. The two waveforms will be delivered simultaneously, but will have different oscillation frequencies. After each two-day period, the warm and cold waveforms will be switched so that the opposite ears will be treated with the different caloric stimulation. Thus every two days the ear receiving the cold stimulus will be switched to the warm stimulus and vice versa.

The following parameters will be set for the placebo treatments using the CVS-M Device:

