- To assess whether BID active treatment provides therapeutic gains over QD active treatment, the reductions in migraine headaches, the reduction in the number of acute (prescribed) medication taken, the reduction in subject-perceived headache pain scores, the normalized percent-change in monthly headache days, and the 50% responder rates in the BID active-treatment subjects and QD active-treatment subjects during the following periods will be compared: the first treatment month, the third treatment month, the sixth treatment month and the final month of the post-treatment period. Additionally, change scores for the QOL measures (HIT-6, BDI, BAI and the Pittsburgh Sleep Quality Assessment) at the end of the first and second treatment periods and the post-treatment observation period will also be assessed. The response kinetics for each of these parameters will be evaluated by comparing time courses for each of the three treatment arms. All change scores will be calculated relative to baseline measures.
- To assess whether six months of active treatment provides improved levels of migraine prevention relative to three months of active treatment, comparisons of the reductions in migraine headache days, the reduction in the number of acute (prescribed) medication taken, the reduction in subject-perceived headache pain scores, the normalized percent-change in monthly headache days, and the 50% responder rates during the third treatment month and the sixth treatment month (relative to baseline) for the QD active and the BID active groups will be performed. Change scores for the QOL measures (HIT-6, BDI, BAI and the Pittsburgh Sleep Quality Assessment) for the QD active and the BID active groups at the end of the first and second treatment periods (relative to baseline) will also be compared. Additionally, these measures will also be compared between the BID active and BID placebo groups during the sixth treatment month. All change scores will be calculated relative to baseline measures.

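### The correlation with sessions actually performed can look like a dose effect when once- and twice-daily treatment are equal, so the dose conclusion should rest on the randomised BID-QD comparison

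*Combined protocol and SAP*

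**What the plan says.** The last item under Secondary Endpoints in section 7 of the combined protocol and SAP reads: "To assess whether the reduction in migraine days relates to the number of active CVS treatments performed, correlational analyses will be performed". The outcome is the change in headache days over each study period, and the question is whether it "is a function of the cumulative CVS treatments performed". A generalised linear mixed model is added, to see whether "the probability of a headache on any given day is predicted by the cumulative number of active treatments performed".

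The count comes from the device log. The note on treatment delivery data in section 4 says: "The SD card data files also record treatment times and subject compliance, which will be used to calculate the level of treatment compliance".

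For these analyses the plan does not say which arms are included. It names no adjustment for arm, baseline headache days or elapsed time, and does not warn that the count is partly the subject's own choice. Section 8 sets a 5% Type I error and does not label these analyses exploratory.

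Dose is also randomised. Section 3 allocates subjects to "twice-per-day active, once-per-day active or twice-per-day placebo in a 1:1:1 ratio". The third aim in the Background is "To test the efficacy of once-per-day active treatments versus twice-per-day active" treatment. A separate secondary endpoint in section 7 begins "To assess whether BID active treatment provides therapeutic gains over QD active treatment, the reductions in migraine headaches", and makes the comparison in "the first treatment month, the third treatment month, the sixth treatment month and the final month of the post-treatment period".

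**The concern.** Every subject in an arm is assigned the same number of sessions per day. Differences in sessions completed within that arm are therefore behaviour after randomisation, and behaviour can follow outcome: a subject who feels no benefit may skip or stop, and one who improves may continue. The plan foresees such variation. It sets a 50% compliance threshold for the per-protocol analysis, expects 5 dropouts per group in each three-month period, and lists lack of efficacy and adverse events as reasons for discontinuation on the Subject Disposition Form.

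A correlation with sessions performed thus mixes the randomised contrast with self-selected adherence. A significant result could be read as dose-response evidence even if QD and BID do not differ. Placed beside a null randomised BID-QD result, it would invite the wrong conclusion on a stated aim of the trial.

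**Working it through.** **Inputs from the documents.** 40 subjects per arm, SD of the reduction 3.36 days, detectable difference 2.13 days, 80% power, alpha 0.05 (section 8); 84 days per treatment period (section 4); reductions of 3.6 and 0.9 days in the first trial (Background).

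**Assumptions.** The documents give no data linking adherence to outcome. Adherence is taken as evenly spread over 50% to 100%, with a correlation rho of 0.2 to 0.4 with improvement within each arm. The section 8 SD refers to month 3 and stands in for the period outcome.

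**The plan's own figure.** A two-sided two-sample t-test with 40 per arm, SD 3.36 and a difference of 2.13 days has power 79.95%. The stated figure reproduces. The plan gives no figure for the correlation.

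**Active arms only, with no QD-BID effect.** Both arms have the same mean improvement of 3.6 days. Sessions in period 1 are adherence × 168 (BID) or × 84 (QD). Share of simulated trials with p<0.05:

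| Analysis | rho 0 | 0.2 | 0.3 | 0.4 |
|---|---|---|---|---|
| Two active arms pooled | 5% | 14% | 24% | 40% |
| BID active alone | 5% | 23% | 45% | 73% |
| Sessions performed, adjusted for arm | 5% | 37% | about 70% | 93% |
| Randomised BID versus QD | 5% | 5% | 5% | 5% |

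**Check by hand at rho 0.3.**
- BID alone, n = 40: atanh(0.3) × √37 = 0.3095 × 6.083 = 1.88. P(Z > 1.96 − 1.88) is about 47%.
- Pooled, n = 80: the adherence variance is 0.5²/12 = 0.0208. The within-arm variance of the count is 0.0208 × (168² + 84²)/2 = 367.5. The mean counts are 126 and 63, so the between-arm variance is 31.5² = 992. The total is 1,360 (SD 36.9), of which 73% comes from assignment. The pooled correlation is rho × 0.1443 × 126/36.9 = 0.49 × rho = 0.148. Then 0.149 × √77 = 1.31, and P(Z > 0.65) is about 26%.

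Pooling therefore dilutes the bias without removing it. Adjusting for arm strips out the randomised part of the variation and leaves the self-selected part, so the error rises.

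**Sensitivity.** With mean adherence 80% and SD 0.12 or 0.20, the pooled figures are 10-15% at rho 0.2 and 18-29% at rho 0.3. With rho −0.3 the pooled test is significant in about 24% of trials, nearly always against the device.

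**Placebo included with zero active sessions.** Take QD equal to BID, both better than placebo by d days, and no adherence link. For d = 2.13 (section 8) the correlation is significant in about 76% of trials; for d = 3.6 − 0.9 = 2.7 (Background), about 92%. By hand for d = 2.13:
- covariance 21 × 2.13 = 44.7;
- SD of the count √(245 + 2,646) = 53.8;
- SD of the outcome √(3.36² + 2 × 2.13²/9) = 3.51;
- r = 44.7/(53.8 × 3.51) = 0.237, and atanh(0.237) × √117 = 2.61, giving about 74%.

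**Regression on assigned sessions.**
- End of period 1, coded 0/84/168 for placebo/QD/BID with equal arms: the deviations from the mean are −84, 0 and 84, so the slope is 84 × (BID mean − placebo mean)/(2 × 84²) = (BID mean − placebo mean)/168. The QD mean cancels. With QD equal to BID, this slope is significant in about 79% to 95% of trials over the same range of d.
- End of period 2, coded 168/168/336: the deviations are −56, −56 and 112, so the slope is [BID mean − (QD mean + placebo mean)/2]/168. The placebo arm received its 168 active sessions in one period and the QD arm over two, so dose is mixed with timing.

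**The case against.** The strongest reply is that the plan already handles dose by randomisation. A reader might infer from the sessions-performed item that the randomised dose goes unanalysed. The documents do not support that: BID versus QD is an aim and a named secondary endpoint, and in simulation it keeps its 5% error throughout. Nothing in section 7 says that the correlation would override it. What remains is that the plan does not say which result carries the dose conclusion.

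A second reply is that size and direction are assumed. That stands. A reader might infer that the bias must favour the device, but subjects with more headaches may treat more and improved subjects may relax. The documents contain nothing that settles the sign.

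A third is that the highest rates belong to versions the plan does not name, namely BID alone and adjustment for arm. That is fair. The pooled active-arm figures are the milder reading, and they still run from about 14% to 40%. The plan does not say which version will be run.

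Fourth, section 8 limits diary endpoints to subjects with at least 25 entries in the relevant month, so those who stop the diary as well as the device would leave the analysis. The mechanism then works mainly through subjects who cut sessions but keep recording.

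Finally, this is one of many secondary endpoints and is worded as correlational. The primary endpoint is unaffected.

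**Conclusion.** The concern holds for the sessions-performed analyses only. As written, they can give a significant result with no difference between QD and BID: about 14% to 40% of trials with the active arms pooled and 23% to 73% in BID alone, at an assumed adherence-improvement correlation of 0.2 to 0.4 in either direction. If placebo zeros are pooled, the figure is about 76% to 92% with no adherence link at all, because an active-versus-none difference then appears as dose-response. The daily model uses the same kind of count and has the same weakness; it was not simulated.

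A reader might also infer that regressing outcome on assigned sessions would repair this. It would not: the first coding reproduces BID versus placebo, and the second mixes dose with timing of exposure. The randomised BID-QD comparison is the sound source for the dose conclusion. The plan contains it but does not link it to this analysis.

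**What to change.** Before unblinding, add to section 7 or 8:

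- The conclusion on dose rests on the randomised BID-active versus QD-active comparison already listed among the secondary endpoints.
- The correlation and the mixed model on sessions performed are descriptive and non-causal. They are reported within each active arm, without placebo zeros and without a significance claim for dose.
- Neither adjustment for arm alone nor a regression on 0/84/168 or 168/168/336 assigned sessions serves as the dose test.

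The cost is a few sentences of SAP text and no new data. The downside is that sessions performed can no longer support an inferential dose-response claim, so the dose question depends on a comparison for which the trial was not sized. If the 3.36-day SD applies, that comparison has 80% power for a BID-QD difference of 2.13 days with 40 per arm, 2.28 days with 35 and 2.47 days with 30, the last two following from 5 dropouts per group in each later period.
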